1.3 Hypothesis

Hypothesis: FNB is superior compared to FNA for whole exome sequencing and genomic profiling of tissue sampling of pancreas cancer.

1.4 Benefit/Risk Aspects

Procedures used in this study are standard medical practice for the evaluation of lesions within or adjacent to the GI tract. The shark core FNB is an FDA approved device for sampling of submucosal lesions, mediastinal masses, lymph nodes and intraperitoneal masses. FNB was introduced as a less invasive alternative to open surgical biopsy. FNB has been proposed to increase the sampling yield and proposed to potentially require fewer needle passes compared to conventional FNA. This could potentially improve the tissue yield which is measured by the tumor DNA and will facilitate to perform whole exome sequencing of pancreas cancer. This will provide significant development for “personalized cancer therapy”.

2. STUDY OBJECTIVES

2.1 Primary Objective:

To compare EUS guide fine needle biopsy versus fine needle aspiration for whole exome sequencing and genomic profiling in tissue sampling of pancreatic solid tumors.

2.2 Secondary Objectives:

- To compare the DNA yield of FNB versus FNA in tissue sampling of pancreas cancer including sufficient DNA to complete un-amplified whole exome sequencing.
- To compare the number of needle passes necessary to obtain adequate tissue sample to make a cytological/histological diagnosis when FNB is used as compared to the conventional FNA for pancreas cancer
- To compare the histology quality of the specimens obtained via FNB as compared to conventional FNA.
- To compare the yield of tissue sufficient for targeted (Foundation Medicine Assay) genomic profiling of pancreas tumors.
- To estimate the safety profile of FNB as compared to conventional FNA. (by historical comparison)
- Per needle adequacy for cytology

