5.2 Post-Procedure Evaluations

All of the participants of the study will receive the standard post-EUS care until discharge. Any adverse effects of the procedure will be assessed immediately after procedure and during the first 30 days with a follow-up phone call.

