8.2 Study Protocol

- 1) Filling the “Pre-Procedure Patient Registration” section of the “Registration and Data Collection” form
- 2) Review of the signed informed consent before the start of procedure.
- 3) All patients will undergo conscious sedation or Monitored Anesthesia Care (MAC) for the duration of the procedure. Conscious section and/or MAC are the standard method of sedation for all patients that have EUS at our institution, unless contraindicated.
- 4) Morphologic features of the lesion will be examined and documented in the procedure report. Based on the location and type of the lesion, the participating endosonographer determines the necessity of performing an FNA. If FNA deemed necessary, the patient will be included in the study.

- 5) Randomization of needle order. The first needle to be used will be selected by randomization using block randomization in envelopes (FNA first, FNB first) by tumor location (1 block for head tumors, 1 block for body/tail tumors).
- 6) Conventional FNA will be alternated with FNB (22 gauge for all sites) in the usual fashion for obtaining histological material. A minimum of 2 passes (1 with each needle) will be obtained from all lesions. Conventional FNA will be performed with a standard 25g needle (our standard needle) in the usual fashion using back and forth passes for 30 seconds. Negative pressure will be applied for both needle types using the “capillary” technique of withdrawing the stylet slowly (5-10cm per second) during the to and fro movement of the needle. All FNA material will be expressed onto a glass slide. Visible core samples will be removed and placed in formalin after an initial “touch prep” (light touch of tissue to slide). The presence or absence and length (in mm) of grossly visible each core will be recorded by the cytotechnologist/study personnel. Standard passes (alternating with each needle) will be repeated in pairs until an adequate sample is obtained or the endoscopist feels that no further sampling is warranted. Then, a 2nd and 3rd set of passes (one with each needle) will be performed to collect material for biobanking and DNA and RNA extraction. The sample will be expressed into a sealed biospecimen container and flash frozen in liquid nitrogen, then stored at -80C. If no material is obtained, the research pass will be repeated up to a maximum of 2 passes for each needle.

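### The safety objective sets FNB against historical FNA, but the trial can observe only the adverse-event rate of combined FNA, FNB and research sampling

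*Combined protocol and SAP*

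**What the plan says.** One of the six secondary objectives in section 2.2 is "To estimate the safety profile of FNB as compared to conventional FNA. (by historical comparison"). The protocol names no historical cohort, event rate, number of passes or method for this comparison, and section 9.1 contains no safety analysis.

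Section 8.2 sets the exposure:

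- Item 5 randomises only which needle goes first ("Randomization of needle order"). There is no FNB-only or FNA-only arm.
- Item 6: "A minimum of 2 passes (1 with each needle) will be obtained from all lesions".
- Further diagnostic sampling also uses both needles: "Standard passes (alternating with each needle) will be repeated in pairs until an adequate sample is obtained", or until the endoscopist stops. No upper limit is given.
- After that, "a 2nd and 3rd set of passes (one with each needle) will be performed to collect material for biobanking and DNA and RNA extraction". If no material is obtained, "the research pass will be repeated up to a maximum of 2 passes for each needle".

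On ascertainment, section 5.2 says: "Any adverse effects of the procedure will be assessed immediately after procedure and during the first 30 days with a follow-up phone call". The form described in section 8.1 captures immediate complications and mentions no attribution to a needle or pass. The only safety summary described is an overall rate of anticipated complications, in section 6.3 (reviewed biannually) and section 8.2 item 12 (reviewed quarterly).

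Section 6.1 withdraws patients with a serious immediate complication. Section 3.5 replaces non-completers but keeps their existing data.

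**The concern.** A historical comparison can supply the FNA side of the contrast. It cannot supply the FNB side, because no patient has FNB alone. The rate this trial produces belongs to a procedure with two needle types and added passes that would not be done outside the study. Section 8.1 also lets the endoscopist change to another needle if 2 passes have not given an adequate sample, so some patients may be exposed to a third device.

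Two separate errors could follow if the objective is reported as written:

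- An excess over the historical rate could be blamed on FNB when it comes from the second needle or the research passes. This is confounding, and it works mainly against FNB.
- A low count could be read as evidence that FNB is as safe as FNA. This comes from imprecision at 50 patients, not from the two-needle design.

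**Working it through.** **The plan's own figures.** There is no safety figure to reproduce. The only power statement, in section 9.1, concerns DNA adequacy. With 50 pairs and an exact two-sided McNemar test at 0.05, I get 81.2% (25% difference, 38% discordant) and 80.8% (20% difference, 25% discordant). These agree with the stated 80% or higher but do not bear on safety.

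**Passes per patient (section 8.2 item 6, taking one diagnostic pair).**

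- Plain reading: one diagnostic set plus a 2nd and 3rd set, two needles each: (1 + 2) × 2 = 6.
- Narrower reading: one research pass per needle, with a second only if the first yields nothing: (1 + 1) × 2 = 4, rising to 6 with repeats.
- Additional diagnostic pairs raise either figure. Termination under section 5.1 can lower it.

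**Why the rate does not isolate FNB.** The documents give no event rates, so those below are assumptions. Let pF and pB be the risks from the FNA and FNB parts of the procedure, acting independently. The observable rate is

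p = 1 − (1 − pF)(1 − pB).

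- pF = 1%, pB = 2%: p = 1 − 0.99 × 0.98 = 2.98%.
- pF = 2%, pB = 1%: p = 1 − 0.98 × 0.99 = 2.98%.

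The same observed rate fits opposite rankings of the needles.

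**Size of the confounding with no needle difference (pF = pB).**

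| Assumed risk per needle | Two-needle rate |
|---|---|
| 1% | 1 − 0.99² = 1.99% |
| 2% | 1 − 0.98² = 3.96% |
| 3% | 1 − 0.97² = 5.91% |

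The rate is about double the single-needle rate. If risk instead accrues per pass, at an assumed 0.25% per pass, p = 1 − (1 − 0.0025)^k gives 0.75% for k = 3, 1.00% for k = 4 and 1.49% for k = 6.

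**Precision at n = 50.** The exact (Clopper-Pearson) 95% limits are the 2.5% point of Beta(x, n − x + 1) and the 97.5% point of Beta(x + 1, n − x). For x = 0 the upper limit is 1 − 0.025^(1/50) = 7.1%.

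| Patients with an event | Observed | Exact 95% CI |
|---|---|---|
| 0/50 | 0% | 0 to 7.1% |
| 1/50 | 2% | 0.05 to 10.6% |
| 2/50 | 4% | 0.5 to 13.7% |

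If the true combined rate were 5%, the chance of seeing no event would still be 0.95^50 = 7.7%; at 3% it is 0.97^50 = 21.8%.

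**Power against a fixed historical rate.** With an exact one-sided test at 0.025, assumed historical rates of 1%, 2% and 3% need at least 3, 4 and 5 events to reject. Power to detect a doubling is then 8%, 14% and 18%.

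**The case against.** The strongest reply is that little rests on this objective. It is secondary, its verb is to estimate, no test is planned, the synopsis lists only adverse events as the aim, and sections 6.3 and 8.2 already describe a single overall rate. That stands, and it limits the weight of the point. It does not remove the mismatch, because section 2.2 still promises a comparison of FNB with FNA.

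Four stronger readings are tempting, and the documents do not support them:

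- *That no FNB-specific information could be obtained at any sample size.* The first needle is randomised, and section 5.1 stops the procedure for an immediate complication such as perforation or extensive bleeding. An event at the first puncture follows exposure to one needle, so it is attributable in principle if the needle is recorded. Delayed events, such as pancreatitis or infection found at the 30-day call, are not.
- *That the design biases the comparison in both directions.* A second needle and extra passes would be expected to add events, not remove them. False reassurance comes from the small sample.
- *That every patient certainly has at least six passes.* This is the plain reading of item 6 but not the only one. The sentence on repeating the research pass also allows four.
- *That section 1.4 contradicts section 8.2 on the number of passes.* Section 1.4 gives no study pass count. It says only that FNB might need fewer passes. The document that omits the research passes is the synopsis.

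**Conclusion.** The objective is wrong as written. The observable quantity is the 30-day adverse-event rate of combined FNA, FNB and research sampling. Compared with an FNA-only history, it confounds needle type with the second needle and the added passes, mainly to the disadvantage of FNB. Under assumed equal single-needle risks of 1% to 3%, the design alone roughly doubles the rate. That size depends on the assumed rates and on independence; the direction needs only that extra passes do not reduce risk.

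On that same assumption, the combined rate is a conservative upper bound for the FNB passes given in this study. The bound is loose: even 0/50 leaves an upper limit of 7.1%, which would not establish that FNB is as safe as FNA.

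The primary comparison and its power are unaffected.

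**What to change.** 1. Reword the objective in section 2.2: *To describe the 30-day adverse-event rate of combined FNA plus FNB sampling, including research passes, with exact 95% CI, in all patients punctured.*
2. Add this analysis to section 9.1. State that patients withdrawn under section 6.1, and those replaced under section 3.5, stay in the safety denominator and that their events count.
3. Drop the FNB-versus-FNA safety conclusion.
4. Record on the data collection form the total passes per patient and, for immediate events, the needle in use.
5. Reconcile the synopsis, which omits the research passes, with section 8.2 item 6, and make item 6 unambiguous about how many research passes each needle makes.

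The cost is a few wording changes and a small addition to the form, with no added patients or visits. The trial gives up a comparative safety statement that its design cannot support.

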3. STUDY POPULATION

3.1 Number of Patients:

50

3.2 Inclusion criteria

- Male and female patients who are 18 years old or older and are referred for the evaluation of pancreatic solid mass requiring FNA or FNB.
- International normalized ratio (INR) less than 1.5 and platelet count of more than 50,000.
- Medically stable to undergo sedation for EUS.
- Signed informed consent.

3.3 Exclusion criteria:

- Any medical condition that preclude the patient from having a therapeutic procedure regardless of the EUS finding.
- Pregnant patients.

3.4 Patient Informed Consent

The Institutional Review Board (IRB) of Mayo Clinic will approve a consent document with information about the nature and possible adverse events of the procedure. Patients that might be

included in the trial will be given sufficient time to study the written consent form and ask questions before signing the consent document.

3.5 Replacement Policy

Any patient who does not complete the study will be replaced. In the case of any withdrawal or dropouts, existing data will be retained for evaluation at the end of trial.

3.6 Compensation and Financial Responsibility

Since this procedure is “standard of care”, the cost of procedure will be charged to the patient or their insurer. The cost of the FNB will be covered by a grant from Medtronic Corporation (grant application in process).

3.7 Patient Remuneration

No patient remuneration will be provided for this study.

4. PRE-PROCEDURE EVALUATION

4.1 History and Physical Examination (all standard of care)

- 1) Inclusion/Exclusion Criteria
- 2) Medical History
- 3) Medication Review
- 4) Brief Physical Examination (heart, lungs, abdomen) with vital signs (BP, pulse), and weight

4.2 Laboratory Studies

- 1) CBC and INR (within 30 days of enrollment which is standard of care)

5. INTRA AND POST- PROCEDURE EVALUATION

5.1 Evaluations during Procedure

Standard monitoring, including continuous cardiopulmonary evaluations, will be performed during the EUS exam. In case of immediate complications, including but not limited to, visceral perforation or extensive bleeding, the procedure will be terminated and appropriate standard care will be provided. The precise time for each FNA procedure as defined by the first puncture attempt to the completion of expressing the cytologic material on the glass slide and formalin.

5.2 Post-Procedure Evaluations

All of the participants of the study will receive the standard post-EUS care until discharge. Any adverse effects of the procedure will be assessed immediately after procedure and during the first 30 days with a follow-up phone call.

6. SUBJECT WITHDRAWAL AND STUDY TERMINATION CRITERIA

6.1 Subject Withdrawal

Subjects will be withdrawn from the study for any of the following reasons:

- 1) Voluntary withdrawal - Any patient may remove himself from the study at any time without prejudice to his medical care.
- 2) Complication related Withdrawal - Any patient with a serious immediate complication due to the EUS-FNA will be withdrawn.

6.2 Confidentiality

Only the investigators and their office staff will have access to the data that identifies the patient by name. Patients will be identified only by Standardized Numerical Identifier (SNI) and patient identity will remain confidential if material from the record is used for publication or for educational purposes.

6.3 Interim Analysis

No interim analysis is planned. Biannually the available data will be reviewed retrospectively and the rate of anticipated complications will be calculated. Serious adverse events including any life threatening events, inpatient hospitalization or prolongation of existing hospitalization or any unanticipated complication including any death as a result of the procedure will be reported to the Mayo Clinic IRB.

7. ETHICS AND REGULATORY

7.1 Institutional Review Board (IRB)

Mayo Clinic Institutional Review Board Committee (IRB) will review the study protocol and any amendments. The IRB will review the subject informed consent form, their updates (if any) and any written materials given to the subjects.

7.2 Regulatory Authority Authorization-Approval-Notification

The regulatory permission to perform the study will be obtained in accordance with applicable regulatory requirements. All applicable ethical and regulatory approvals will be available before a subject is exposed to any study-related procedures, including screening tests for eligibility.

7.3 Ethical Conduct of the Study

This study will be conducted in accordance with the ethical principles that have their origins in the Declaration of Helsinki, in compliance with the approved protocol, Good Clinical Practice (GCP) and applicable regulatory requirements.

7.4 Subject Information and Consent

The Investigator (or designee) will obtain a freely given written consent from each subject after appropriate explanation of the aims, methods, potential risks, and any other aspects of the study, which are relevant to the subject's decision to participate. The consent form must be signed and dated by the subject before conducting any study-related procedures, including screening tests for eligibility.

The Investigator will inform the subjects that they are completely free to refuse to enter the study or to withdraw from it at any time, without any consequences to their further care and without a need to justify. The subject will receive a copy of his/her signed informed consent.

Each subject will be informed that portions of his/her source records and source data related to the study may be reviewed and utilized in the study analysis. Data protection will be handled in compliance with Mayo Clinic bylaw.

7.5 Confidentiality of Subject Data

The Investigator will ensure that the confidentiality of the patients' data will be preserved in a safe database. The patients will not be identified by their names, but by SNI, which consists of their initials and number in the study.

7.6 Standardized Numerical Identifier (SNI)

Each subject will be assigned an identifier that will be used for identification purposes. SNI consists of the patient's initials, a ten digit number that correlates with the date and time of the procedure and the initials of the participating investigator in the following format:

I	I	I	M	M	D	D	Y	Y	H	H	M	M	I	I	I
---	---	---	---	---	---	---	---	---	---	---	---	---	---	---	---

Patient initial

Date

Time

Inv. Initial

8. STUDY DESIGN:

This is a single-center, prospective randomized controlled trial. All male and female patients 18 years old or older that are referred for evaluation of pancreatic solid mass can be considered for this trial.

8.1 Patient Registration and Documentation

Recruitment of patients will be initiated at the time of pre-procedure evaluation by one of the investigators. Any patient that has been referred to undergo an EUS exam for one of the above mentioned indications will be consulted regarding the ASPEN trial and his/her questions will be answered. If he/she is interested, the consent form will be provided to the patient and he/she will be asked to sign the consent form to participate in the study.

Patient registration section of the “Registration and Data Collection” form will be completed prior to performing FNA by the investigator. At this point, each patient will be assigned with a Standardized Numerical Identifier (SNI) that will be used for identification and data entry purposes in the study database. This form is designed to collect the following information (See Appendix A):

- Participants name and date of birth and medical record number
- Name of the investigator performing the EUS exam
- SNI
- Type of the cross-sectional study or endoscopic exam that warranted the EUS evaluation
- Size, location and characteristic of the abnormal lesion

After the EUS exam, the investigator will complete the post procedure information section of the “Registration and Data Collection” form that collects the following information (Appendix A):

- Size, location and characteristic of the lesion based on the EUS exam
- Size and type of the needle that was used for conventional FNA (25-gauge needle). 25g needle (brand of needle will be physicians choice) will be used as the standard needle for this study. If an adequate sample is not obtained after a total of 2 passes, the endoscopist may change to a different needle of their choice.
- Immediate complications that were noticed during the procedure or during the recovery period

8.2 Study Protocol

- 1) Filling the “Pre-Procedure Patient Registration” section of the “Registration and Data Collection” form
- 2) Review of the signed informed consent before the start of procedure.
- 3) All patients will undergo conscious sedation or Monitored Anesthesia Care (MAC) for the duration of the procedure. Conscious section and/or MAC are the standard method of sedation for all patients that have EUS at our institution, unless contraindicated.
- 4) Morphologic features of the lesion will be examined and documented in the procedure report. Based on the location and type of the lesion, the participating endosonographer determines the necessity of performing an FNA. If FNA deemed necessary, the patient will be included in the study.

- 5) Randomization of needle order. The first needle to be used will be selected by randomization using block randomization in envelopes (FNA first, FNB first) by tumor location (1 block for head tumors, 1 block for body/tail tumors).
- 6) Conventional FNA will be alternated with FNB (22 gauge for all sites) in the usual fashion for obtaining histological material. A minimum of 2 passes (1 with each needle) will be obtained from all lesions. Conventional FNA will be performed with a standard 25g needle (our standard needle) in the usual fashion using back and forth passes for 30 seconds. Negative pressure will be applied for both needle types using the “capillary” technique of withdrawing the stylet slowly (5-10cm per second) during the to and fro movement of the needle. All FNA material will be expressed onto a glass slide. Visible core samples will be removed and placed in formalin after an initial “touch prep” (light touch of tissue to slide). The presence or absence and length (in mm) of grossly visible each core will be recorded by the cytotechnologist/study personnel. Standard passes (alternating with each needle) will be repeated in pairs until an adequate sample is obtained or the endoscopist feels that no further sampling is warranted. Then, a 2nd and 3rd set of passes (one with each needle) will be performed to collect material for biobanking and DNA and RNA extraction. The sample will be expressed into a sealed biospecimen container and flash frozen in liquid nitrogen, then stored at -80C. If no material is obtained, the research pass will be repeated up to a maximum of 2 passes for each needle.
- 7) After each pass of needle, the on-site cytotechnologist will evaluate the adequacy and the degree of the pathological changes in the obtained material. Based on the information provided by the cytotechnologist, the endosonographer will repeat the FNA until enough material is obtained to confirm the clinical diagnosis. The initial determination of adequacy will be made by the onsite cytotechnologist. The final determination of cytological adequacy will be made by the study pathologist (AN) based on the criteria below.
- 8) Separate sets of slides and formalin jars will be produced in the GI suite from the tissue obtained from each type of the needle. Each pass will be placed on separate slides and

formalin jars with labelling (A, B). 9) In order for the pathologist to remain blinded of the needle type that the tissue was obtained with, two separate slide sets will be generated and each set will be labeled as “*Slide Set A or B*”. Slides that are prepared from the FNB will be labeled as “*Slide Set B*” depending on the parity of the assigned SNI number. Slides that are prepared from the conventional FNA needle will be labeled as “*Slide Set A*” to complete each pair 10) Pathology interpretation for clinical purposes will be done by the on-call pathologist of the day, using all material available. For study purposes a single study pathologist (AN) will interpret all of the slides. The pathologist will evaluate the slides for cell quantity (adequate vs. scanty/acellular), grade of dysplasia (atypical vs. malignant cells), and presence of core samples.

11) Each slide set (A or B) will be evaluated and reported separately for research purposes and accumulatively to generate the patient’s pathology report for medical records.

12) Quarterly, the available data will be reviewed retrospectively and the rate of anticipated complications will be calculated. Anticipated complications of EUS with FNA include, but are not limited to post-procedure pancreatitis, bleeding, perforation, and infection. Serious adverse events from FNA are rare but include life threatening events, inpatient hospitalization, prolongation of existing hospitalization or any unanticipated complication including death as a result of the procedure will be reported to Mayo Clinic IRB.

13) DNA extraction and quantification: One or two biopsy tissues are first digested, then DNA extractions will be performed using the silica membrane-based column DNA extraction method with the QIAamp DNA Mini Kit. This column based extraction method provides purified DNA which is free of protein, nucleases and other contaminants or inhibitors. This kit is used for fresh or frozen tissue, cells, and blood. If larger tissue samples are obtained; the Puregene DNA extraction will be used and is a salt precipitation method. Tissues are lysed and DNA is precipitated from the cells. This method allows for purification of high molecular weight DNA for downstream use.

For DNA quantification, the Trinean DropSense96 spectrophotometer will be used which is a multichannel spectrophotometer for quick and precise UV/VIS spectral analysis of microliter droplets of DNA. This method allows for the measurement of total and double stranded DNA as well as purity and quality ratios (A260/280 and A260/230).

For whole exome sequencing, a minimum of 1.1 ug of DNA is needed (personal communication, [name]; Department of Laboratory Medicine). Thus for this study purpose, 1.1 ug of DNA will be considered a “sufficient” sample. Whole exome sequencing, using a minimum of 1.1 ug of DNA, sequencing will be performed using sequence type: Exome Sure Select v5 + UTR (71MB) at 50% on target (PE 101 base) on the Version 4 HiSeq instrument.

In order to validate that WES can be performed a subset of 5 samples from each needle will be evaluated by whole exome sequencing using Illumina standard methods. Only samples with at least 5 micrograms of DNA will be evaluated. The WES will be performed in a de-identified manner and will not be used clinically for the care of the patient.

14. All the pathological data collection will done by following guidelines from the Papanicolaou Society of Cytopathology Guidelines^{21, 22}.

8.3 9. STATISTICAL CONSIDERATIONS

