9.1 Statistical Analysis

This is paired sample study of FNB vs FNA for whole exome sequencing and genomic profiling. For descriptive analyses, continuous variables will be reported as a mean \pm SD or median (interquartile range) and comparison between two groups will be done by Paired *t*- test. Categorical variables will be reported as frequencies with percentages and compared using chi-square test or Fisher’s exact test. Two sided P values less than 0.05 will be considered statistical

significance. Descriptive analysis will be performed in terms of DNA yield per sample, histology and cytology yield per sample. Sample size calculation is done after interim analysis. **Sample**

size calculation:

From our preliminary data from 5 PDAC patients and using the Foundation Medicine adequacy criteria, 2 (40%) had an adequate sample of DNA with FNA, while all 5 (100%) patients had adequate DNA with FNB. Although this is a very small sample size it is consistent with the notion that FNB may be much superior to FNA. Based on this preliminary data, it seems reasonable to expect that the difference in proportions of adequate samples by the two methods might be 25% or more. Assuming we have 50 patients who all are sampled with both FNA and FNA, then with a McNemar's test we will have 80% or higher power to detect a difference in adequacy proportions between FNA and FNB (at the 5% significance level) of $\geq 25\%$ if $\leq 38\%$ of patients have discordant results for FNA and FNB, or a difference of $\geq 20\%$ if $\leq 25\%$ are discordant. The following are just 3 of many possible examples of scenarios whereby we will have sufficient power with a sample size of 50 patients, all of which are consistent with the findings in the preliminary data:

Example A (25% difference):

		FNA adequate?		
		Yes	No	
FNB adequate?	Yes	$\geq 58.5\%$	$\leq 31.5\%$	90%
	No	$\leq 6.5\%$	$\geq 3.5\%$	10%
		65%	35%	

Example B (25% difference):

		FNA adequate?		
		Yes	No	
FNB adequate?	Yes	$\geq 48.5\%$	$\leq 31.5\%$	80%
	No	$\leq 6.5\%$	$\geq 13.5\%$	20%
		55%	45%	

Example C (20% difference):

		FNA adequate?		
		Yes	No	
FNB adequate?	Yes	$\geq 68\%$	$\leq 22\%$	90 %
	No	$\leq 2\%$	$\geq 8\%$	10 %
		70 %	30 %	

References:

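### Needle order is the only randomised factor, but the paired t-test for DNA quantity leaves it out, so any order effect stays in the error term and costs power

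*Combined protocol and SAP*

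**What the plan says.** Section 8.2, item 5, randomises needle order by "block randomization in envelopes (FNA first, FNB first) by tumor location", with "1 block for head tumors, 1 block for body/tail tumors". Item 6 has the two needles alternate, at least one pass each. Paired passes continue until the sample is adequate or the endoscopist stops. Further sets of passes, one per needle, then supply the frozen material for biobanking and DNA and RNA extraction. The text does not say whether these research passes keep the randomised order.

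For continuous variables, section 9.1 says that "comparison between two groups will be done by Paired" t-test, and the synopsis says the same. For categorical variables both name chi-square or Fisher's exact test. McNemar's test appears only in the sample-size paragraph. No analysis text mentions order, period, sequence or tumour location. The synopsis does speak of stratifying by lesion location, but it is describing how passes are taken.

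DNA yield is a secondary objective in section 2.2 and a listed aim in the synopsis. Section 8.1 lists lesion location among the form's fields but does not list needle order.

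**The concern.** The design is a within-patient crossover of needle order. Taking the difference between needles removes whatever is common to the patient and lesion, including the main effect of tumour location. It does not remove an effect of going first or second. That effect raises the FNB-minus-FNA difference in one order group and lowers it by the same amount in the other.

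A paired t-test pools the two groups and treats the gap between their means as random scatter. The standard error is then too large and the test rejects too rarely. The protocol controlled this factor by design, and with only 50 pairs it gives up that benefit if the analysis ignores it.

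**Working it through.** **The plan's own figure.** Section 9.1 claims at least 80% power for McNemar's test with 50 pairs, for a 25-point difference with 38% discordant or a 20-point difference with 25% discordant. The exact test at two-sided 0.05 gives 81.2% (split 31.5% / 6.5%) and 80.8% (split 22.5% / 2.5%). The claim reproduces. It concerns adequacy; the plan gives no power figure for DNA quantity.

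**Inputs for DNA quantity.**
- From the documents: 50 pairs, two-sided 5% level, paired t-test.
- Assumed: within-order SD of the paired difference = 1; needle effect = 0.4 SD; 25 patients per order; order effect k, the first-pass-minus-second-pass advantage, of 0, 0.25, 0.5 or 0.75 SD.

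**Model.** D = 0.4 + k + error when FNB is first; D = 0.4 − k + error when FNA is first.

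**Step 1: bias.** With 25/25 order the mean of D is 0.4 for every k, so there is none.

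**Step 2: error variance.** The expected sample variance of D is 1 + k² × 50/49. That is 1.064, 1.255 and 1.574 at k = 0.25, 0.5 and 0.75; the square roots are 1.031, 1.120 and 1.255.

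**Step 3: power of the planned test.** The true standard error of the mean is still 1/√50, so the standardised effect is 0.4 × √50 = 2.828. The critical value on 49 df is 2.010, and the inflated standard error multiplies it. Power is approximately Φ(2.828 − 2.010 × √variance).

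| k | Calculation | Approximate power | Simulated, paired t-test | Simulated, order fitted |
|---|---|---|---|---|
| 0 | Φ(0.819) | 79.4% | 79% | 79% |
| 0.25 | Φ(0.756) | 77.5% | 77% | 79% |
| 0.5 | Φ(0.577) | 71.8% | 72% | 79% |
| 0.75 | Φ(0.307) | 62.1% | 62% | 79% |

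Fitting order removes k from the error variance. The critical value on 48 df is 2.011, giving about Φ(0.818) = 79.3% at every k.

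**Step 4: type I error.** The planned test's actual two-sided rate is 4.3%, 2.8% and 1.4% at k = 0.25, 0.5 and 0.75, against a nominal 5%.

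**Sensitivity.** With the needle effect at 0.404 SD, which gives 80% power at k = 0, planned power is 78.3%, 72.9% and 63.6% at the same three values of k, against 80.0% with order fitted.

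**Step 5: unequal order groups.** With n₁ patients in one order, the unadjusted estimate shifts by k(2n₁ − 50)/50. That is 0.08k at 27/23 and 0.20k at 30/20.

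**The case against.** **The size is unknown.** The documents give no SD for DNA yield and no order effect. The drop from 79% to 72% needs an order effect larger than the assumed needle effect. At 0.25 SD the loss is about 2 points. This stands: the mechanism is certain, its size is not.

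**The DNA comes from later passes.** Both needles have already been through the lesion before the research passes, and nothing says those passes follow the randomised order. This also stands. The order term must describe the passes that supplied the DNA, and their order is not among the form fields listed in section 8.1.

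**The powered comparison is elsewhere.** The sample size rests on adequacy and McNemar's test, where fitting order gains little when order is balanced. This is right and limits the point to a secondary outcome.

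**Stronger readings a reader might infer.**
- *The needle estimate is biased.* With balanced order it is not, and the test is conservative. Material bias needs both a marked imbalance and a large order effect. In simulations with 15 to 35 head tumours (an assumption), a 30/20 split or worse never occurred with block sizes 4 to 10. It occurred in 0.03% of trials with size 20 and 6% with size 50. Block size is not stated, so exact balance is not assured, but 30/20 is a stress case. At 27/23 and k = 0.25 the shift is 0.08 × 0.25 = 0.02 SD.
- *Omitting tumour location is an equal fault.* Its main effect cancels within the pair. It matters only if the needle difference itself varies by location, which the documents do not suggest.
- *Adequacy needs an order-adjusted conditional logistic model.* Only discordant pairs inform that model, and it has no finite estimate if either order group lacks one kind of discordant pair. With 25 patients per order, the rarer kind (6.5% in Example A, 2% in Example C) is absent from at least one group with probability 1 − (1 − 0.935²⁵)² = 34% or 1 − (1 − 0.98²⁵)² = 84%.

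**Conclusion.** The point holds as a modest, nearly free gain in precision for the DNA-quantity comparison. The plan randomises needle order and then leaves it out of the paired t-test. The loss is nil without an order effect, about 2 points of power at 0.25 SD, 7 at 0.5 SD and 17 at 0.75 SD. This rests on 50 pairs, balanced order, a needle effect of 0.4 SD, and DNA passes that follow the randomised order. The last is an assumption the protocol should turn into a stated rule. The finding does not show bias in the needle comparison, a flaw in the adequacy analysis, or a shortfall in the stated sample size.

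**What to change.** In section 9.1, replace the paired t-test for DNA quantity with a linear model of each patient's FNB-minus-FNA difference, on the log scale if yields are skewed, with a stated rule for zero yields. Enter needle order as +1 (FNB first) or −1 (FNA first). The intercept is then the needle effect, weighting the two order groups equally even if their sizes differ. Tumour location, centred, may be added as an optional second term.

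In section 8.2, item 6, state that the research passes supplying the DNA follow the randomised order, and add their actual order to the data collection form.

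Keep McNemar's test for adequacy, as the sample-size paragraph assumes. Any order-adjusted supporting analysis should use an exact or penalised method.

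The cost is one degree of freedom (two with location), a few lines of text and one recorded field. If there is no order effect, power is essentially unchanged.
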